5.2.9. Adequate Post-baseline ALL Disease Assessment

An adequate post baseline assessment is defined as an assessment for hematologic disease status and extramedually disease response (if applicable) has been provided by the investigator. Timepoints where the response is indeterminate or no assessment was performed will not be used for determining the censoring date.

5.2.10. Nominal and Unscheduled Visits

For all algorithms and analyses, visit labels as specified on the CRF will be used as the nominal timepoint (ie, assessment will not be slotted).

Unless otherwise specified, unscheduled assessments will not be displayed in summary tables by nominal visit/timepoint. Unscheduled assessments will be used when deriving baseline and worst case on-treatment for safety analyses (except where noted for baseline ECGs). Additionally, unscheduled assessments will be used for efficacy analyses (eg, defining date of progression/censoring, best overall response, date of last contact).

5.2.11. Standard Deviations and Reporting Conventions

For reporting conventions, mean and median should generally be displayed one more decimal place than the raw data and standard deviation should be displayed to two more decimal places than the raw data. Percentages will be reported to one decimal place. The rounding will be performed to closest integer/first decimal using the common mid-point between the two consecutive values. Eg, 5.1 to 5.4 will be rounded to an integer of 5, and 5.5 to 5.9 will be rounded to an integer of 6.

The following conversion factors will be used to convert days into weeks, months or years:

1 week = 7 days, 1 month = 30.4375 days, 1 year = 365.25 days.

Demographics and physical measurements:

- Age [years]:
 - year of given informed consent - year of birth.
- Body Mass Index (BMI, kg/m²) = weight (kg) / [height (m)]².
- Body Surface Area (BSA, m²) = $0.007184 \times \text{Weight}(\text{kg})^{0.425} \times \text{Height}(\text{cm})^{0.725}$, (Du Bois Formula).

5.2.12. Analyses for Continuous and Qualitative Variables

Continuous variables will be summarized using descriptive statistics, ie, number of non-missing values, mean, median, standard deviation (SD), minimum, maximum and first and third quartile (Q1 and Q3).

Qualitative variables will be summarized by frequency counts and percentages. Unless otherwise specified, the calculation of proportions will include the missing category. Therefore counts of missing observations will be included in the denominator and presented as a separate category.

In case the analysis refers only to certain visits, percentages will be based on the number of participants still present in the study at that visit, unless otherwise specified.

5.2.13. Analyses for Time-to-Event Endpoints

Kaplan-Meier estimates (product-limit estimates) will be presented for treatment arm together with a summary of associated statistics including the median time with two-sided 95% CIs. Probabilities of an event at particular timepoints will be estimated with corresponding two-sided 95% CIs. The CIs for the median will be calculated according to Brookmeyer and Crowley and the CIs for the survival function estimates at particular timepoints will be derived using the log(-log) method.

5.3. Methods to Manage Missing Data

Unless otherwise specified, all data will be evaluated as observed, and no imputation method for missing values will be used.

Any imputations will occur at the analysis dataset level. Additionally, in all data listings imputed values will be presented and flagged as imputed.

Missing statistics, eg, when they cannot be calculated, should be presented as 'ND' for not done, 'NR' for not reached or 'NA' for not applicable. For example, if N=1, the measure of variability cannot be computed and should be presented as 'ND' or 'NA'.

5.3.1. Missing Pharmacokinetic Data

Concentrations below the limit of quantification

For all calculations, all concentrations assayed as below the limit of quantification (BLQ) will be set to zero. The BLQ values will be excluded from calculations of geometric means and their confidence intervals. A statement similar to 'All values reported as BLQ have been replaced with zero' should be included as a footnote to the appropriate tables and figures. In listings BLQ values will be reported as below limit of quantification ("<LLOQ"), where LLOQ will be replaced with the corresponding value from the analytical assay used.

Deviations, Missing Concentrations and Anomalous Values

In summary tables, concentrations will be set to missing if one of the following cases is true:

- A concentration has been reported as ND (ie, not done) or NS (ie, no sample);
- A deviation in sampling time is of sufficient concern or a concentration has been flagged as anomalous by the clinical pharmacologist.

Summary statistics will not be presented at a particular timepoint if more than 50% of the data are missing. For analysis of pharmacokinetic concentrations, no values will be imputed for missing data.

In summary tables of concentration-time profiles or PK parameters, statistics will be calculated by setting NC values to missing; and statistics will not be presented for a particular treatment if more than 50% of the data are not collected, not calculated, or below LLOQ. For statistical analyses (ie, analysis of variance), PK parameters coded as NC will also be set to missing.

If an individual participant has a known biased estimate of a PK parameter (due for example to a deviation for the assigned dose level), this will be footnoted in summary tables and will not be included in the calculation of summary statistics or statistical analyses.

5.3.2. Missing ECG Data

For QTc analyses, no values will be imputed for missing data. If one or two of the triplicate measurements for an ECG parameter are missed, the average of the remaining two measurements or the single measurement can be used in the analyses. If all triplicate measurements are missing at a timepoint for an ECG parameter, no values will be imputed for this timepoint. If the triplicate needs to be repeated because of an artifact, then the repeated triplicate will be reported on an unscheduled CRF page. Based on a review of the

data these unscheduled assessments may be used in place of the assessments at the nominal time. Data review and consultation with the study team is required to flag these cases.

5.3.3. Handling of Incomplete or Missing Dates

5.3.3.1. Adverse Events

AE Onset Date:

The following imputation rules apply if the event is unique for a participant or it is the first of a series of similar events; otherwise, the AE Onset Date will not be imputed:

- If the first active day of study intervention is less than AE stop date, then the onset date will be set to first active day of study intervention;
- Otherwise if the first active day of study intervention is after AE stop date, then set the onset date to the earliest of non-missing AE stop date or informed consent date.

AE Stop Date:

Ongoing events will have the AE Stop Date set to the latest of the subject withdrawal/completion date, death date, last active day of study intervention, or AE Onset date.

Imputation will only occur if event is unique for the participant, or it is the last of a series of similar events; otherwise the Stop Date will not be imputed. Adverse Events are deemed similar if they have the same verbatim term.

Resolved events will have the AE Stop Date set to the AE Onset date.

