3.5.1. Adverse Events

Adverse events (AEs) will be coded to preferred term (PT) and system organ class (SOC) using the Medical Dictionary for Regulatory Activities (MedDRA) and classified by severity using the National Cancer Institutes (NCI) Common Terminology Criteria for Adverse Events (CTCAE), version 5.0. For other AEs without specific NCI CTCAE v5.0 definitions, results will be identified according to NCI CTCAE v5.0 “other” categories.

An event will be considered treatment related if the investigator considers so.

An adverse event is considered treatment-emergent relative to a given treatment if the event start date is during the on-treatment period (including on the date of first dose). All cases of VOD/SOS irrespective of causality or severity will be reported as SAEs for up to 2 years after the first dose of inotuzumab ozogamicin.

Adverse Events of Special Interest (AESI)

AEs of special interest (AESI) are as follows:

- GRADE ≥ 3 HEPATOTOXICITY AND/OR SERIOUS HEPATOTOXICITY, INCLUDING VOD/SOS;
- MYELOSUPPRESSION/CYTOPENIA;
- INTERSTITIAL LUNG DISEASE;
- INFLAMMATORY GASTROINTESTINAL EVENT;
- PANCREATITIS;
- SECONDARY PRIMARY MALIGNANCY;

- REPRODUCTIVE AND DEVELOPMENT TOXICITY;
- NEPHROTOXICITY; and
- NEUROTOXICITY.

These events are defined in [Appendix 2](#).

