5.3.3.3. Date of Death

Missing or partial death dates will be imputed based on the last contact date:

- If the date is missing it will be imputed as the day after the date of last contact.
- If the day or both day and month is missing, death will be imputed to the maximum of the full (non-imputed) day after the date of last contact and the following:
 - Missing day: 1st day of the month and year of death;
 - Missing day and month: January 1st of the year of death.

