6.6.1. Adverse Events

All analyses will be based on treatment emergent events unless otherwise specified. Treatment emergent is defined in [Section 3.5.1](#). AEs not considered treatment emergent will be flagged in data listings.

A high level summary of TEAEs (all causality), TEAEs (treatment related) and Cycle 1 TEAEs (treatment related) will include the number and percentage of participants with:

- Any TEAE;
- Serious TEAE;
- TEAE with CTCAE Grade 3-4;
- Grade 5 TEAE;

- TEAEs leading to dose reductions of inotuzumab ozogamicin;
- TEAEs leading to dose delay of inotuzumab ozogamicin;
- TEAEs leading to permanent discontinuation of inotuzumab ozogamicin.

Additionally, the number of events reported for each of the categories above will be provided. Each unique adverse event at the PT level for a participant is included in the count.

Seriousness, toxicity grade, action taken (interruption, reduction, and withdraw) are as reported by the investigator on the adverse event CRF.

Summaries of TEAE by SOC and PT in decreasing frequency will be provided for:

- TEAEs (All Causality);
- TEAEs by Maximum Toxicity Grade (All Causality);
- TEAEs (Treatment related);
- TEAEs by maximum toxicity grade (Treatment related);
- Serious TEAEs (All causality);
- Post-HSCT SAE (All causality);
- Serious TEAEs (Treatment related); and
- Post-HSCT SAE (Treatment related).

An event will be considered treatment related if the investigator considers so.

The following summaries will be provided by PT only (ie, summaries will not include SOC) in decreasing frequency:

- TEAEs (All causality);
- TEAEs (All causality) experienced by $\geq 10\%$ of participants;
- TEAEs (All causality) by maximum toxicity grade;
- Grade 3-5 TEAEs (All causality and Treatment related);
- TEAEs leading to dose delays of inotuzumab ozogamicin (all causality);
- TEAEs leading to dose reductions of inotuzumab ozogamicin (all causality);

- TEAEs leading to permanent discontinuation of inotuzumab ozogamicin (all causality);
- Serious TEAEs (all causality); and
- Post-HSCT SAEs (all causality).

Each participant will be counted only once within each SOC and PT.

As described in [Section 5.3](#), in case a participant has events with missing and/or non missing toxicity grades, the maximum of the non-missing grade will be displayed. Missing grade will only be displayed in the event that only one event has been reported for a participant and the grade is missing.

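### The rule for incomplete AE onset dates ignores a recorded month and year, so some late, post-window or pre-dose events are dated to the first dose

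*SAP*

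**What the plan says.** SAP 5.3.3 deals with incomplete and missing dates together, and 5.3.3.1 is its rule for adverse events.

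- **Scope.** The rule covers only an event that is unique for the participant or opens a series of similar ones. For any later event in a series, "otherwise, the AE Onset Date will not be imputed". Events are similar if they share a verbatim term.
- **Branch 1.** When the first dose falls strictly before the end of the event, "then the onset date will be set to first active day of study intervention".
- **Branch 2.** If the first dose is after the stop date, the onset is the earlier of the stop date and the consent date.
- **Stop dates.** Ongoing events take the latest of several dates, normally after first dose, so most fall under branch 1. For the rest, "Resolved events will have the AE Stop Date set to the AE Onset date".

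The onset date then decides classification. SAP 3.5.1: "An adverse event is considered treatment-emergent relative to a given treatment if the event start date is during the on-treatment period", with the date of first dose counted as on treatment. SAP 3.5 ends that period at the earlier of 9 weeks after the last dose and the day before new anti-cancer therapy. Data outside it are listed but, unless otherwise specified, not summarized. SAP 6.6.1 plans a high-level summary in which TEAEs "and Cycle 1 TEAEs (treatment related) will include the number and percentage of participants with" the listed event categories, and also separate post-HSCT SAE tables.

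By contrast, for a partial death date SAP 5.3.3.3 starts from the known parts: "Missing day: 1st day of the month and year of death". SAP 5.3.3.5 does the same for start dates, but only for dates that have no rule of their own.

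**The concern.** A record that gives month and year but no day still carries most of the information about when an event began. Branch 1 has no term for it. The only question asked is whether the event ended after first dose, which is true of nearly every event on this study.

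Three things depend on the onset date: whether an event is treatment-emergent and so enters the main tables, which cycle it belongs to, and possibly whether it precedes or follows transplant. AE timing is part of the safety endpoint (Protocol Section 3; SAP 2.1), and Protocol 9.4.2 asks for VOD in total, on treatment and post-HSCT. Partial dates are plausible in long-term follow-up: VOD is collected for 2 years, disease visits are 12 to 24 weeks apart, and survival contact may be by telephone or email.

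**Working it through.** The plan states no figure for this rule, so there is none to reproduce. The check applies SAP 5.3.3.1 literally, with SAP 3.5 and 3.5.1, to illustrative dates.

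**On-treatment window, nominal timing (21-day Cycle 1, later cycles 28 days)**
- Two cycles: last dose on Day 21 + 15 = 36; window ends on Day 36 + 63 = 99.
- Six cycles: last dose on Day 21 + 4 × 28 + 15 = 148; window ends on Day 148 + 63 = 211.
- Transplant example: transplant on Day 36 + 34 = 70 (the 34 days approximate the 4.9-week median in Protocol 2.2.2.1.1). Conditioning is assumed to start 7 days earlier, on Day 63, and to count as new anti-cancer therapy. The window then ends on Day 62.

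**Cases.** First dose is 10 Jan 2023. Study days follow SAP 5.2.3 (date − first dose + 1 from first dose onward; date − first dose before it). Month and year of onset are recorded; the day is missing. The comparison rule takes the first of the known month, or the first dose date if that month contains it and the stop date is not earlier. TE = treatment-emergent.

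| Case | True onset | Window end | SAP rule | Month-aware rule |
|---|---|---|---|---|
| Cycle 5 event, stop Day 125 | Day 115, TE | Day 211 | Day 1, TE, Cycle 1 | Day 112, TE, Cycle 5 |
| SAE after transplant, stop Day 100 | Day 85, not TE | Day 62 | Day 1, TE | Day 82, not TE |
| VOD, stop Day 420 | Day 400, not TE | Day 62 | Day 1, TE | Day 388, not TE |
| Pre-dose onset, stop Day 10 | Day −21, not TE | Day 99 | Day 1, TE | Day −40, not TE |
| Pre-dose onset, stopped before dose | Day −21, not TE | Day 99 | Earlier of stop and consent, not TE | Day −40, not TE |
| Stop date equals first dose | Day −5, not TE | Day 99 | No branch applies | Day 1, TE by convention |
| Later episode, same verbatim term | Day 30, TE | Day 99 | No onset date, status undefined | Day 23, TE |

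Month-aware days: 1 May 2023 is 111 days after first dose (Day 112); 1 Apr 2023, 81 days (Day 82); 1 Feb 2024, 387 days (Day 388); 1 Feb 2023, 22 days (Day 23); 1 Dec 2022 is 40 days before (Day −40). The Day 23 result assumes the first episode was not later than that. Consent is taken to precede the pre-dose onset; it does not enter branch 1.

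The Day 85 case depends on the conditioning assumption, since without it the window runs to Day 99. The Day 400 case does not.

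**Range of displacement.** On nominal timing an on-treatment onset can move back by up to 211 − 1 = 210 days, and a VOD onset by up to about 2 years.

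**Circular case.** A resolved event with an unknown stop date takes its onset as its stop. If the onset is also incomplete, branch 1 needs the stop date first, so neither can be derived.

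**The case against.** The strongest case on the other side is that the practical reach is small and the error cautious.

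- **Most non-serious events change only in timing.** Non-serious AE recording stops at new anti-cancer therapy (Protocol 8.4.1.2), and general collection need run only 9 weeks past the last dose. That nearly matches the on-treatment window. This stands: wrong treatment-emergent status mainly concerns SAEs, VOD and pre-dose events that continue past first dose. The Cycle 1 summary is also limited to treatment-related events.
- **Listings flag imputed values (SAP 5.3), and assigning unclear onsets to first dose errs toward counting them.** True, but the SAP requires no such flag in tables, and an onset with a known later month is not unclear in the way that matters.
- **VOD is unlikely to be recorded by month only.** It is reported as an SAE within 24 hours of awareness and adjudicated, and its criteria need day-level dating. This is fair, so the VOD row shows what the rule does, not how often.

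Four stronger readings are tempting, and the documents do not support them:

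- *Any incomplete onset goes to Day 1.* Branch 2 keeps events that ended before first dose pre-treatment, and later same-term episodes are not imputed.
- *Repeat events drop out.* The SAP leaves their status undefined; it does not exclude them. Counting once per SOC and PT limits the effect, except where the undated episode is the worst-graded, serious, related or only on-treatment one.
- *AE dates alone discard known parts.* Under SAP 5.3.3.2, a last-dose date with known month and an earlier year than the end-of-treatment or death date falls through to that later date, so it loses the month as well.
- *About a fifth of VOD cases would be moved.* B1931022 rates imply 44 × 79/164 × 18/79 = 4.8 post-HSCT cases, but the fraction simply assumes that one of them has a partial date.

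**Conclusion.** The point holds in this form: SAP 5.3.3.1, followed literally, gives a wrong onset for a unique or first event that has a partial onset date and a stop date after first dose, unless the event truly began on the first-dose day. For later on-treatment events the error is in timing and cycle. For SAEs and VOD that begin after the window, and for pre-dose events that end after first dose, it also changes treatment-emergent status. If post-HSCT status is derived from the onset date, which the SAP does not define, the event also leaves the post-HSCT tables; total VOD counts need not change.

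Three situations have no workable rule: an incompletely dated later episode, a stop date equal to first dose, and a resolved event with both dates incomplete.

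The size cannot be computed, because the documents give no frequency of partial AE dates; it could be nil. The table rests on chosen dates and nominal cycle lengths. The CR/CRi analysis is untouched, and the safety analyses are descriptive. The rule is still worth correcting because it produces a wrong result and the correction is cheap.

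**What to change.** Rewrite SAP 5.3.3.1 to use the known parts first:

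1. **Month and year known:** first of that month, or the first dose date if that month contains it and the stop date is not earlier.
2. **Year only:** 1 January of that year, or the first dose date on the same conditions applied to the year.
3. **Completely missing:** the first dose date if it is on or before the stop date; otherwise keep the present branch 2. Changing the strict comparison to on-or-before closes the equal-date gap.
4. **Limits:** never impute an onset later than the stop date. Apply the rule to repeat episodes too, but not earlier than the preceding episode of the same term.
5. **Transplant month:** if the known month contains the HSCT date, take pre- or post-HSCT status from the CRF or adjudication record. First-of-month alone would put an onset recorded only as March before a transplant on 5 March. In B1931022 the median time from HSCT to VOD was 15 days (range 3 to 57), so this is realistic.
6. **Resolved events with a partial stop date:** last day of the known month, not before onset; otherwise leave it missing. This removes the circularity.

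The cost is SAP wording and a few lines of derivation code before database lock. No new data are needed beyond confirming that the CRF or adjudication record holds HSCT status for such events.

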5.3.3.2. Exposure

No imputation will be done for first dose date. Date of last dose of study treatment, if unknown or partially unknown, will be imputed as follows:

- If the last date of study treatment is completely missing and there is no Disposition page with Phase= “Treatment” and no death date, the participant should be considered to be ongoing and use the data cutoff date for the analysis as the last dosing date; or
- If the last date of study treatment is completely or partially missing and there is EITHER an EOT CRF page OR a death date available (on or prior to the data cutoff date), then impute this date as the last dose date:
 - = 31DECYYYY, if only Year is available and Year < Year of min (EOT date, death date),
 - = Last day of the month, if both Year and Month are available and Year = Year of min (EOT date, death date) and Month < the month of min (EOT date, death date), or

= min (EOT date, death date), for all other cases.

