**Table 1. Schedule of Activities**

Protocol Activity	Screen  -28 days from enrollment	Cycles 1-6			End of Treatment (EOT)  (All patients: 4 weeks from the last dose of study drug)
		Day 1	Day 8	Day 15	
Study Visit Window (Days)		±2	±2	±2	±3
Informed consent & Participant ID number & Distribute emergency contact card	X				
Eligibility criteria	X				
Contraception check	X	X			X
CD22 Immunophenotyping 	X				
Antibodies to inotuzumab 		X			X
Demography/Medical History	X				
Weight/height 	X	X			X
Vital Signs and Physical Examination 	X	X	X	X	X
ECOG performance status (PS)	X				X
Laboratory Assessments: During the treatment period, all laboratory assessments must be done within 72 hours prior to dosing.					
Hematology 	X	X	X	X	X
Blood Chemistry 	X	X	X	X	X
Urinalysis 	X				X
Coagulation 	X	X			X
Pregnancy test 	X	X			X
HbsAg and anti- hepatitis C virus (HCV) 	X				

PFIZER CONFIDENTIAL

CT02-GSOP Oncology Clinical Protocol Template (01 April 2022)

Page 20

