2. INTRODUCTION

This SAP provides the detailed methodology for summary and statistical analyses of the data collected in study B1931034. This document may modify the plans outlined in the protocol; however, any major modifications of the primary endpoint definition or its analysis will also be reflected in a protocol amendment.

Any deviations from this analysis plan will be described in the Clinical Study Report (CSR).

The primary analysis will include all data up to a data cutoff date which is at least 9 months after last participant first dose. The final number of enrolled participants might deviate from the planned number. All summaries and analyses will include all data pertaining to assessments performed up to and including the data cutoff date.

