3.4. Baseline Variables

Start and end dates of study treatment:

The date of first dose (start date) of study treatment is the earliest date of non-zero dosing of the study drug.

The date of last dose of study treatment is the latest date of non-zero dosing of the study drug.

Definition of baseline:

No windowing will be applied when defining baseline.

For efficacy analyses and baseline characteristics associated with tumor assessments, the last assessment prior to the first dose will serve as the baseline assessment.

For safety (including Eastern Cooperative Oncology Group (ECOG) performance status) and immunogenicity the last assessment performed on or prior to date of the first dose of study treatment will serve as the baseline assessment. If there are no observations meeting these criteria, then baseline is considered missing.

Participants who start treatment and discontinue from the treatment on the same day may have two different sets of data collected on study day 1 (one during study and one in the End of Treatment (EOT) visit. Data reported at the EOT visit are not eligible for baseline selection.

Triplicate ECGs are collected; therefore the baseline for each ECG measurement is the average of the pre-dose triplicate measurements reported on during screen period or closest to the start date. Unscheduled assessments will not be included in the calculation of the average. If the last prior to Cycle1/Day 1 ECGs are triplicate ECGs (or only 2), they will be averaged. If the last prior to Cycle1/Day 1 ECG is a single, that will be used as baseline. Baseline heart rate (HR), derived from RR measured in seconds as 60/RR if RR is collected, and QT/QTc interval assessments will be derived from the visit where both HR and QT are not missing. QTcF (Fridericia's correction) and QTcB (Bazett's correction) will be derived based on RR and QT. The average of the replicate measurements will be determined after the derivation of the individual parameters at each timepoint.

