5.2.4. Definition of Cycle and Cycle Day

Cycle start and end dates are derived per participant and not per study treatment.

Study drug inotuzumab ozogamicin is administered once every week for 3 weeks (on Days 1, 8, and 15) for each cycle. Except for Cycle 1 where a 7-day treatment free interval is optional, all other cycles have such an interval following the 3 treatment administrations and hence the nominal cycle length is 21-28 days for cycle 1 and 28 days for other cycles. A participant can only go through 6 cycles at most.

- For Cycle X, the actual cycle start date for each participant is:
 - The earliest start date of dosing in the Cycle X day 1 visit CRF exposure page, if the participant received study treatment on that visit (ie, any study drug with dose>0 at that visit).
 - The first day of assessments in the Cycle X day 1 visit, if the participant did not receive study treatment on that visit (ie, all study drugs had dose=0 at that visit). Use start date in the exposure page if available; if start date is not available then use date of collection of vital signs on Cycle X day 1 visit.
- For all but the last cycle,
 - Actual cycle stop date is calculated as the start date of the next cycle minus one day.
 - Actual cycle duration is calculated from Day 1 of a cycle to the day prior to Day 1 of the next cycle, as follows:

$$\text{Actual Cycle Duration (weeks)} = (\text{cycle stop date} - \text{cycle start date} + 1) / 7.$$

- For the last cycle, actual cycle duration is the planned cycle duration and actual cycle stop date is calculated as min(actual cycle start date + 28 – 1 day, new anti-cancer therapy date-1, death).

The cycle day will be calculated as:

Cycle day = Date of the assessment/event – cycle start date + 1.

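### SAP 5.3.3.2 has no branch for a last dose known by month and year in the calendar year before EOT or death, so the catch-all replaces the recorded month with the EOT or death date

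*SAP*

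**What the plan says.** SAP 3.4 defines the date: "The date of last dose of study treatment is the latest date of non-zero dosing of the study drug". SAP 5.3.3.2 is the fallback when that date is unknown or partly unknown.

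If there is an EOT page or a death date, 5.3.3.2 has three branches:

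- Year only, earlier than the year of min(EOT, death): 31 December of the recorded year.
- Month and year: "Last day of the month, if both Year and Month are available and Year = Year of min (EOT date, death date"), provided the recorded month also precedes the EOT or death month.
- Otherwise: "min (EOT date, death date), for all other cases".

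If the date is wholly missing and there is neither a treatment disposition page nor a death date, then "the participant should be considered to be ongoing and use the data cutoff date for the analysis as the last dosing date".

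Four other places bear on how these branches behave:

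- Protocol Table 1 sets the EOT visit at "4 weeks from the last dose of study drug", with a ±3-day window. Footnote 19 requires it before any new anti-leukemic therapy.
- SAP 2 sets "a data cutoff date which is at least 9 months after last participant first dose".
- SAP 5.2.4 states: "A participant can only go through 6 cycles at most".
- SAP 5.3.3.4, which imputes the start of new anti-cancer therapy, has a branch for a recorded month in an earlier year. It gives the last day of that month.

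**The concern.** A month recorded by the site is information, and an imputation rule should not override it. Here it does so whenever the final infusion and the EOT or death date fall either side of a year end. The parallel rule in SAP 5.3.3.4 covers this case, so the gap looks like an omission rather than a choice. A programmer following the text would produce a date that the data contradict.

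The same catch-all, and the cutoff default, place a wholly missing last dose at an administrative date that normally falls well after the final infusion. Three outputs depend on the last-dose date: treatment duration (SAP 6.5.3.1), the 9-week limb of the on-treatment window (SAP 3.5), and the table of deaths within and after 28 days of last dose (SAP 6.6.2). In the cases worked below the error is never early, so averaging over participants does not remove it.

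**Working it through.** The plan gives no figure on this point to reproduce. The check applies the rule as written, reading EOT date as the visit date.

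**1. Recorded month in the earlier year.** Example: infusions on 1, 8 and 15 December 2023 (Days 1, 8 and 15); final date recorded as December 2023 with no day; participant alive; EOT 28 days later, on 12 January 2024.

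- Year-only branch: not met, because the month is known.
- Month branch: not met, because 2023 is not 2024.
- Catch-all: last dose = 12 January 2024, 28 days late.
- Treatment duration = (last − first + 1)/7. True: 15/7 = 2.1 weeks. Imputed: 43/7 = 6.1 weeks.
- Nominal window end: 63 + 28 = 91 days, or 13 weeks, after the true last dose instead of 9.
- Under a branch like that in 5.3.3.4: 31 December 2023, which is 16 days late and keeps the recorded month.

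With EOT at 28 days, last doses on 4 to 31 December cross into January. That is 28 of 31 December dates, or 28/365 = 7.7% of day-missing dates if last doses are spread evenly over the year. For EOT at 25 to 31 days the share is 25/365 = 6.8% to 31/365 = 8.5%.

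**2. All incomplete-date patterns.** The rule was applied to each of the 365 possible last-dose dates in a year, with EOT 28 days later and the participant alive:

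| What is missing | Mean days late | Range |
|---|---|---|
| Day | 15.8 | 0 to 28 |
| Day and month | 26.9 | 0 to 28 |
| Whole date | 28.0 | 28 |

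For a wholly missing date the excess is 25 to 31 days across the visit window. Adding the earlier-year branch lowers the day-missing mean only from 15.8 to 14.7 days. Its value is that no recorded month is overridden; it does nothing for wholly missing dates.

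**3. Cutoff default.**

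- Nine months at the SAP's 30.4375 days per month: 9 × 30.4375 = 273.9 days; 273.9/7 = 39.1 weeks. This is a minimum, since earlier participants have longer follow-up.
- Nominal Cycle 6 Day 15: 5 × 28 + 15 = day 155 (22.1 weeks), or 21 + 4 × 28 + 15 = day 148 (21.1 weeks) if Cycle 1 lasts 21 days.
- Excess over the longer nominal course: 39.1 − 22.1 = 17.0 weeks.
- With delays: Protocol 7.1.1.1 lets the next Day 1 fall up to 42 days after the previous Day 15. Used at every cycle, this puts Cycle 6 Day 15 at 5 × (14 + 42) + 15 = day 295, beyond day 274.

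**4. Effect on summaries, per affected participant among 44.**

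- A 28-day error moves mean duration by 4.0/44 = 0.09 week.
- The cutoff default moves it by at least (39.1 − 22.1)/44 = 0.39 week if the true duration was the nominal maximum. If the true duration was 8.9 weeks (the median in study B1931022, Protocol 2.2.2.1.3), the shift is at least (39.1 − 8.9)/44 = 0.69 week.
- With a 28-day error, a death 40 days after the true last dose is tabulated at 40 − 28 = 12 days and changes row. So would any death from day 29 to day 56 (28 + 28).

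**The case against.** The case for leaving the rule alone is mostly that it will seldom be used and that its reach is narrow. Much of that stands.

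- **Rare trigger.** Protocol 6.5 has the date and time of each in-clinic dose entered in source and CRF. The year-end problem needs a missing day as well as a year-end crossing. The cutoff default needs a wholly missing date, no treatment disposition page and no death date together.
- **EOT date is undefined.** If it means the treatment-discontinuation date, the 28-day figure does not apply. If it means the visit, an EOT brought forward before new therapy (Table 1, footnote 19) shortens the excess, as does an earlier death.
- **Safety counts.** A reader might infer that treatment-emergent event counts would be inflated across the board. The documents do not support that. The window also closes the day before new anti-cancer therapy (SAP 3.5). Adverse events are generally collected only to about 9 weeks after the actual last dose (Protocol 8.4.1, a stated minimum). The main exception is VOD/SOS, which is reported for 2 years and summarised separately in any case (SAP 6.6.1.1).
- **Exposure.** A reader might infer that exposure as a whole is overstated. Only treatment duration uses this date; cumulative dose, dose intensity and relative dose intensity are built from doses and cycles (SAP 6.5.3.1).
- **SAP 3.4.** It is tempting to see a conflict with SAP 5.3.3.2. There is none: one defines the date and the other is its missing-data fallback.

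None of this supplies the missing branch. A recorded month in the earlier year is still overwritten.

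**Conclusion.** The defect is real and minor. SAP 5.3.3.2 as written replaces a recorded month with the EOT or death date when the two fall in different calendar years. In the worked case the date is 28 days late, assuming that EOT is the on-schedule visit and comes before any death. Under the same assumption, a wholly missing last dose is 25 to 31 days late. The cutoff default assigns at least 39 weeks against a nominal maximum of about 22. A reader might conclude that nobody could still be receiving doses at cutoff; that holds only on the nominal schedule, since permitted delays can reach day 295.

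The consequences stop at treatment duration, the nominal on-treatment limit and the 28-day death split. A further route, through the last-dose term in SAP 5.3.3.4, needs the start of new therapy to be incomplete as well. The primary CR/CRi test does not depend on this date.

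**What to change.** Edit SAP 5.3.3.2 in three places:

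1. **Add the missing branch.** When month and year are recorded and that year precedes the year of min(EOT date, death date), impute the last day of the recorded month, as SAP 5.3.3.4 does.
2. **Define EOT date.** State whether it is the visit date or the treatment-discontinuation date.
3. **Use the infusion records when the final date is wholly missing.** Impute from the recorded infusions: never earlier than the latest recorded non-zero infusion and never later than min(EOT, death, cutoff). This replaces the default to the EOT visit or the data cutoff.

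A simple back-calculation, such as the earlier of the previous infusion plus 7 days and EOT minus 28 days, should not be used for step 3. It has no floor: if EOT is brought forward to 7 days after the final infusion, EOT minus 28 falls 21 days before that infusion and can precede a recorded dose. It also ignores the 14 days from Day 15 to the next Day 1 in a 28-day cycle.

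The cost is SAP wording and one derivation. No new data are needed, and the primary endpoint definition and analysis are unchanged.
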